Rationale: Altered glucose and fat metabolism is most apparent in the post-prandial state, in terms of insulin resistance, β-cell failure, hyperglycemia and DNL. Our preliminary data indicates that glucose and insulin concentrations are most different between 3-4 hours following a glucose load.

The optimal timing post-drink to describe metabolomics differences is not known.

Methods: Targeted metabolomics profiles will be performed at intervals during the OGTT to determine time points that provide the biggest difference in girls with HS, hyperglycemia, inadequate β-cell response and IR. Specific targets will likely be free fatty acid and DNL markers, and will be determined from on ongoing pilot study.

II. Background and Significance:

a) Overall background:

Polycystic Ovarian Syndrome (PCOS) affects 6-10% of U.S. women, with an estimated economic burden of \$4 billion, and is increasing in prevalence in parallel with the obesity epidemic^{1,2}. PCOS includes elevated androgens, and higher rates of insulin resistance (IR), type 2 diabetes (T2D), nonalcoholic fatty liver disease (NAFLD) and cardiovascular disease (CVD)³⁻⁶. The increasing rates of obesity-related PCOS are a major contributor to the earlier onset and rising incidence of T2D, NAFLD and CVD³⁻⁷. Current PCOS therapies are marginally efficacious, and one of them, oral contraceptives, may adversely affect CVD risk⁸⁻¹⁴. *Despite the high prevalence and serious morbidity associated with PCOS, a gap exists in the current therapeutic options.*

b) Mechanisms of insulin resistance in PCOS

Alterations in hepatic metabolism may be central to IR and cardiometabolic disease in PCOS.

[figure not shown]
An estimated 50-70% of obese women with PCOS have NAFLD, compared to 20-30% of obese women without PCOS ^{7,15}. Furthermore, obese women with PCOS and NAFLD are more IR than those without NAFLD, indicating a link between NAFLD and worsening IR in PCOS ⁴. Liver enzyme concentrations, as a marker of NAFLD, independently predict dysglycemia and T2D onset¹⁶, and a new NAFLD medication decreased dysglycemia¹⁷, arguing for a tight connection between glycemia and liver health. In obese non-PCOS youth, NAFLD correlates with adipose, hepatic and muscle IR, is worsened by fructose consumption, and reversed by weight loss¹⁸⁻²¹. Animal models of primary

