We had a pilot study to perform a limited number of inpatient polysomnograms in another of our current protocols, 14-0542, which has identical inclusion criteria. Just analyzed results from 14-0542 indicate the there is a strong relationship between obstructive sleep apnea (OSA) defined as an apnea hypopnea index (AHI) of 5 events per hour or greater and fatty liver disease. Girls with OSA also had higher serum triglycerides and glucoses 2 hours after the glucola drink, despite similar BMI's (Table 1).

	Mean AHI (apnea/hour)	BMI %ile	Hepatic fat fraction (>5.5% = fatty liver)	Serum TG, mg/dL (>150 abnormal)	2 hour glucose, mg/dL (>140 pre-diabetes)
AHI >5, N=13	14.6±3.5	98±1	10.5±2.6	162±19	153±6
AHI < 5, N=13	1.3±0.4	97±1	5.3±1	110±12	131±5

Further, at least 50% of the girls studied had mild to moderate obstructive sleep apnea, and a few had severe sleep apnea, although there was a bias to performing sleep studies in girls with symptoms suggestive of OSA, so this is not a true prevalence estimate from this obese female population. Clinically, from the PI's PCOS clinic, approximate 1/3 of obese girls with PCOS are requiring continuous positive airway pressure therapy for OSA. Thus, it may be that the presence and severity of sleep apnea is a confounder for our primary outcome of altered hepatic metabolism. Accordingly, we need to quantify the presence and severity of OSA in all of our subjects to be enrolled in 16-2399.

Traditionally, inpatient overnight polysomnograms are performed in youth, to determine OSA. However, through our experience in performing these with protocol 14-0542, these can only be performed at Children's Hospital Colorado on Thursday nights, which greatly limits scheduling and enrollment. Additionally, whereas the price for these was \$500 a piece, this has now been

changed, and is currently nearly \$2,000 per patient, as a research price. Due to these limitations, we have sought alternative means of quantifying the degree and severity of OSA.

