A wearable sleep device, WatchPAT, designed for home use has been utilized for the last 5 years clinically in adults. In July of 2016, the FDA approved the use of this device down to the age of 12 specifically for the oxygen saturation and apnea hypopnea index, but not the respiratory disturbance index (>17 years only). We have included the device company provided general description of the device, as well as the descriptions of limitation and use with individuals 12-17 years. As many of the limitations of pediatric use pertain to placement and utilization of the device, we will perform the sleep study while the patients are having their already planned and approved overnight stay in the hospital, and will have the device placed by our study personnel, who will be trained in correct placement and interpretation. Our study team also has extensive experience with similar devices from this company, and they are a supportive and easy to work with company.

Known obstructive sleep apnea or treatment with CPAP will not be an exclusion criteria, however, those individuals already utilizing CPAP at home will be requested to bring it for admission and use it during the WatchPAT study, so that we capture their typical home sleep patterns.

III. Research Methods

A. Outcome Measure(s):

Primary Outcome Measure(s): Activity ratios of the hepatic pentose phosphate pathway, TCA cycle and TG synthesis.

Secondary Outcome Measure(s): Peripheral IR as assessed with a 6.5 hour OGTT, measures of SNS activity, Hepatic fat content, hepatic phosphate profile. Targeted glucose and fat metabolism metabolomics, and untargeted exploratory analysis, gut microbiota profile.

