VISIT 2 (MRI/CV VISIT)

Overall Plan: UCD Research MRI (Brain Imaging Center): Subjects will be asked to fast for 4-6 hours prior to this visit. The imaging will be of the liver. Two different studies may be conducted. One will be standard MRI of the mid abdomen to assess the amount of subcutaneous fat, visceral fat and percent liver fat. The second type of scan is optional pending scheduling. It will be ^{31}P spectroscopy to measure the concentrations of phosphate molecules including PDE, PME and PCr. This will be done twice, before and 30-45 min following a standard 75 gram glucose load. The MRI time is approximately an hour in a 2 hour visit. Vascular Endothelial function and Heart Rate Variability will be assessed with Endopat and Dynapulse, which take approximately 30 minutes.

^{31}P MRS of the Liver and Abdominal Imaging (pending scheduling)

[figure not shown]
MRS Data acquisition: Imaging and MRS will be performed on a Siemens 2.9 Tesla MRI magnet. A custom $^1\text{H}/^{31}\text{P}$ abdominal coil will be used for imaging and MRS (Clinical MR Solutions, Brookfield, WI) as in our previous ^{31}P work⁴⁰. The coil will be a concentric probe with an inner coil 16 cm in diameter (for ^{31}P) and a 20 cm outer coil (for ^1H scout imaging and shimming). A 2 cm x 2 cm x 2 cm area of focus is found in the liver in homogenous tissue for MRS, similar to our previous studies³⁸. A ^{31}P MRS scan will then be performed for baseline measurements. We will continue to work with our current collaborators [name], Assistant Professor, Department of Radiology, UC Denver Anschutz and [name], Professor, Department of Radiography, University of Alabama at Birmingham to optimize the MR signal collection. Subjects will then consume 75 grams of glucose and 25 grams of fructose and the scan will be repeated every 10 min for an hour. Visceral adiposity will be measured using the gold standard of an MRI slice at L4-L5. Hepatic fat fraction will be performed using modification of the Dixon method as in our previous studies³⁴. Hepatic fibrosis will be measured with a fibroscan sequence.

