Secondary outcomes include a Pearson correlation test of potentially related variables followed by targeted multiple regression to assess the relationship between hepatic fat and adipose IR, PEP, TCA, TG synthesis pathways.

Non-Isotope OGTT calculations: The Matsuda model of IR will be used but adapted for the 6.5 hour OGTT, and B-cell function [insulinogenic index ($\Delta I30/\Delta G30$) and ($\Delta C30/\Delta G30$) and disposition index ($1/I_{Fasting} \times \Delta I30/\Delta G30$) and ($1/C_{Fasting} \times \Delta C30/\Delta G30$) will be calculated^{38,49,51,52}.

Differences between groups will be evaluated with and without controlling for activity and sleep status.

Fitting glucose and glycerol concentrations curves: Using computed data points, glycerol and glucose concentrations will be fitted with an appropriate model. In control subjects, concentration typically shows 3 phases in OGTT ⁵³. Cubic polynomial, piecewise-linear, spline, and dynamic models have been used for fitting Ra in previous work^{54,55}. We will assume a cubic polynomial model; we will validate estimates obtained with the cubic polynomial model by computing comparable estimates using at least one other model form. In previous work comparing different models (piecewise-linear, cubic polynomial, dynamic), results have been relatively unaffected by choice of model. If we find that this is not the case for our data, then we would certainly consider the advantages of adopting a more complex approach, such as the state-space, for describing concentration changes.

Metabolomics data: Differences in targeted metabolic concentrations will be compared between groups, after appropriate cleaning of the data, as performed by the processing site. Changes in metabolites over time will be compared between groups, to determine the times that demonstrate the largest differences. Results will also be compared to isotopomer results, to see if a metabolomics endpoint can yield similar information to the isotopomer analysis.

Gut Microbiota: The microbiota profile is entirely exploratory, and will be related to status of hepatic steatosis and 2 hour glucose status of impaired glucose tolerance or not.

VIII. Summarize Knowledge to be Gained:

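### The exploratory microbiota analysis uses only yes/no hepatic steatosis and impaired glucose tolerance, although fat fraction and 2-hour glucose are measured on a full scale

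*Combined protocol and SAP*

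**What the plan says.** All references are to the combined protocol and SAP.

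- **Standing of the outcome.** Section III.A lists the microbiota among the secondary outcomes ("untargeted exploratory analysis, gut microbiota profile"). The Gut Microbiota paragraph of section VII states: "The microbiota profile is entirely exploratory". No hypothesis, effect size or power is given for it.
- **Planned analysis.** The same sentence continues that the profile "will be related to status of hepatic steatosis and 2 hour glucose status of impaired glucose tolerance or not". No analysis on the underlying measurements is stated for the microbiota.
- **How the two quantities are measured.** Section III.C, Visit 2: "Hepatic fat fraction will be performed using modification of the Dixon method". Glucose is drawn serially through the 6.5-hour OGTT at Visit 3.
- **The cuts.** They appear only as column headings of the pilot table under the preliminary polysomnogram data: "Hepatic fat fraction (>5.5% = fatty liver") and "2 hour glucose, mg/dL (>140 pre-diabetes"). Section VII defines neither category.
- **Continuous analysis elsewhere.** Section VII plans Pearson correlation followed by multiple regression between hepatic fat and adipose insulin resistance, PEP, TCA and TG synthesis. The microbiota is not named there.

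**The concern.** Reducing a measured quantity to above or below a threshold treats all girls on one side as alike and discards their ordering. With at most 80 completers in four groups of 20, there is little information to spare. A real association between the microbiota and liver fat or post-load glucose is then more likely to be missed. The plan gives no reason for using only the categories here, and it handles hepatic fat as a continuous variable for the flux pathways a few lines earlier.

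**Working it through.** **The plan's own power figures.** None concerns the microbiota; the three given are for flux. A two-sided t test at 0.05 reproduces them:

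| Comparison | Difference / SD | Plan | Reproduced |
|---|---|---|---|
| 15 v 15 | 3 / 2 | 0.97 | 0.977 |
| 20 v 20 | 2 / 2 | 0.87 | 0.869 |
| 30 v 15 | 2 / 2 | 0.87 | 0.871 |

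Two-sided 0.05 is therefore the plan's working convention and is used below.

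**Inputs**
- n = 80: four groups of 20 (section III.B).
- Share above the HS cut: over 45% of obese girls with PCOS in the investigators' earlier data (section VIII, Significance), so close to a median split in those groups.
- Share with impaired glucose tolerance: not given. The pilot table has two groups of 13, with 2-hour glucose 153±6 and 131±5. The share above 140 is 0.5 × P(N(153, s1) > 140) + 0.5 × P(N(131, s2) > 140).
  - If ± is a standard error: s1 = 6√13 = 21.6, s2 = 5√13 = 18.0, share = 0.5 × 0.726 + 0.5 × 0.309 = 0.517.
  - If ± is a standard deviation: share = 0.5 × 0.985 + 0.5 × 0.036 = 0.510.
- Correlation r between the microbiota summary and the continuous measure: not given. Assumed 0.1 to 0.5.

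**Information kept.** For a normal predictor with share p above the cut, r shrinks to r × φ(z_p)/√(p(1−p)), where φ is the standard normal density and z_p the cut point.
- p = 0.50: 0.3989/0.5 = 0.798; squared, 0.64.
- p = 0.45: 0.796; squared, 0.63.
- p = 0.30: 0.759; squared, 0.58.
- p = 0.20: 0.700; squared, 0.49.

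**Power.** Fisher z: power ≈ Φ(atanh(r)√77 − 1.96), plus the negligible other tail. For r = 0.30, atanh(r)√77 = 0.3095 × 8.775 = 2.716, which gives 0.775. With a median cut r becomes 0.239 and power is 0.572.

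| r | Continuous | Median cut | Loss | Loss if 20% above cut |
|---|---|---|---|---|
| 0.1 | 0.142 | 0.108 | 0.034 | 0.048 |
| 0.2 | 0.428 | 0.292 | 0.136 | 0.193 |
| 0.3 | 0.775 | 0.572 | 0.203 | 0.311 |
| 0.4 | 0.961 | 0.827 | 0.134 | 0.247 |
| 0.5 | 0.998 | 0.960 | 0.038 | 0.104 |

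A 45% split gives almost the same losses as the median cut (0.205 at r = 0.3). A check with 20,000 simulated samples at r = 0.31 gave 0.81 continuous against 0.61 at a 45% split, and 0.81 against 0.49 with 20% above the cut.

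**Sensitivity to the spread of glucose.** I simulated the pilot mixture itself (20,000 samples, n = 80, linear relation, r = 0.30).
- Standard-error reading: the yes/no variable correlates 0.80 with glucose; power 0.78 against 0.58, a loss of 20 points.
- Standard-deviation reading: glucose is two-humped and the yes/no variable correlates 0.90 with it; power 0.79 against 0.69, a loss of 10 points.

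**Sensitivity to the shape of the relation.** If the outcome jumps by 0.64 SD exactly at the cut (45% above) and is otherwise flat, the yes/no analysis has power 0.80 and the continuous one 0.60.

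**The case against.** The strongest reply is that the plan declares the microbiota work wholly exploratory and claims no power for it, so nothing promised is broken. That stands, and it limits the weight of the point. It does not explain why an exploratory analysis should discard information already collected.

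HS status is also the study's organising contrast, so reporting the microbiota by HS status is coherent. That stands too, and is a reason to keep the categories in view. It does not support using them alone. The planned Pearson correlations of potentially related variables might be read as covering the microbiota, but the text names only hepatic fat, adipose insulin resistance and the flux pathways.

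The power figures describe one normally distributed summary. The protocol describes community comparison by phylogenetic and OTU-based methods, so the figures are only a guide to the loss for a multivariate profile. The pilot share above 140 may not carry over either. Those girls were chosen partly for sleep-apnea symptoms, and this study also enrols 20 controls without PCOS.

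Two stronger readings are tempting and fail. The first is that Aim 2 metabolomics has the same fault. Aim 2 does seek to "determine time points that provide the biggest difference in girls with HS, hyperglycemia", but it gives no cut-points. Section VII says only: "Differences in targeted metabolic concentrations will be compared between groups". It does not define those groups, which could be the four enrolment groups. The second is that the pilot shows many girls sitting at the cuts. The 5.3% fat fraction is the mean of the 13 girls with AHI below 5, and the other 13 average 10.5%. Group means do not show how many individual girls lie near a threshold.

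**Conclusion.** The concern holds for the microbiota analysis, as a minor and nearly free improvement. The plan relates the profile to two dichotomies of quantities it measures continuously and, for hepatic fat, already analyses continuously elsewhere.

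A reader might take away a flat loss of about 20 points. The documents do not support one number, since they give no effect size and no prevalence of impaired glucose tolerance. What can be said is conditional on a roughly linear relation: about 3 to 20 points for a near-median cut at n = 80, and up to about 31 with 20% above the cut. For glucose at r = 0.30 it is about 10 points if the pilot ± values are standard deviations. Under a pure step at the cut the sign reverses.

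**What to change.** In the Gut Microbiota paragraph of section VII, state that the profile will be related to hepatic fat fraction (transformed if skewed) and to 2-hour glucose as continuous variables. Keep HS and impaired-glucose-tolerance status as descriptive tables, and state there the cut-points used.

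The cost is about two sentences. No samples, visits or data are added, and two continuous predictors replace two yes/no ones, so the number of tests need not grow. The small downside is an assumed linear or log-linear relation, which would lose power if the truth were a step at the cut; the retained tables would help show such a pattern.
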